## CLINICAL TRIAL PROTOCOL SYNOPSIS

Name of company: [REDACTED]		Tabulated Trial Protocol			
Name of finished product: NA					
Name of active ingredient: BI 6727					
Protocol date 03 October 2005	Trial number 1230.1	Planned study period 10/2005 – 02/2007			
Title of study: An open phase I single dose escalation study of BI 6727 administered intravenously in patients with advanced solid tumours with repeated administration in patients with clinical benefit					
Investigator : [REDACTED]					
Study centre : [REDACTED]					
Clinical phase: I					
Objectives: Safety, maximum tolerated dose (MTD), pharmacokinetics, efficacy					
Methodology: Uncontrolled, open label, dose escalation					
No. of subjects entered:					
total:	Up to 80				
each treatment:	3 to 6 per level, 24 at MTD				
Diagnosis and main criteria for inclusion Patients with a confirmed diagnosis of an advanced and/or metastatic solid tumour refractory to standard therapy or not amenable to standard therapies					
Test product(s) : BI 6727					
dose:	Start dose of 12 mg				
mode of admin. :	Intravenous, once every 21 days				
Reference therapy: n.a.					
dose:					
mode of admin. :					
Duration of treatment: Single dose, repeated treatment courses in patients with clinical benefit					
Criteria for efficacy: Tumour response, time to progression, pharmacokinetic profile of BI 6727					
Criteria for safety: Adverse events according to common terminology criteria for adverse events (CTCAE) v.3.0, laboratory evaluations, patient performance, vital signs					
Statistical methods: descriptive statistics					
Kaplan Meier method for time to progression analysis					

## FLOW CHART: INITIAL TREATMENT COURSE

Study Periods	Screening	Treatment	Observation after Treatment						EOT f	FU
			course 1							
Visit	1	2	3	4	5	6	7	8		
Day	-14 - 0	1	2	3	5	8	15	22		
(day range)				(±1)	(±1)	(±1)	(±1)	(±2)		
Informed Consent and Subject Information	x									
Demographics	x									
Genotyping		x j								
Medical History	x									
In- /Exclusion Criteria	x	x								
Physical Examination	x								x	x b
ECOG performance score	x	x						x	x	x
Pregnancy test	x									
MRI, CT a	x							x a		x
EUS, US (optional)	x							x		x
Body weight	x	x							x	
ECG	x	x k						x		x b
Infusion BI 6727	x									
Vital Signs	x	x	x	x	x	x	x	x		
Safety lab parameters	x	x	x	x	x	x	x	x		x b
Tumour markers i	x							x		
Urine examination	x		x						x	
Pharmacokinetics (plasma)		x c	x c	x c	x c	x c	x c			
Pharmacokinetics (urine)		x h	x h	x h						
Adverse Events	x	x	x	x	x	x	x	x	x	x e
Concomitant Therapy	x	x	x	x	x	x	x	x		
Tumour assessment a	x							x a		x
Conclusion of Subject Participation									x	

a according to RECIST guidelines. Imaging and assessment are required at the end of every other treatment course.b optionalc for time schedule of pharmacokinetic sampling refer to table (Appendix 10.2), plasma samples have to be drawn from the opposite arm of the infusion. For patients having central venous access, BI 6727 may be administered using this device and PK samples obtained from either forearm. Intensive PK blood sampling performed in Course 1 only; for repeated courses PK blood sampling performed at the end of infusion (1:00h) after 24:00h, 168:00 h and after 336:00h (Appendix 101.2).e if not yet recovered at the end of the previous course and in case of new adverse events if drug relatedf end of treatment; investigations which have to be performed at the last visit (when a patient discontinues the study)g data from visit 8 may be used in case EOT examinations were done within the past four weeks

FU= follow up visits until progression, lost to follow up or treatment with another anti-cancer drug

h one blank urine will be sampled prior to the infusion on visit 2 (at least two 2 mL aliquots), additionally urine will be collected for 24 h intervals (0-24 and 24-48 h)

i in applicable tumour types of the underlying disease (c.f. 5.2.5)

j Six (6) mL blood collected into an EDTA tube and processed as outlined in Appendix 10.3.3 for Cytochrome P450 (CYP2D6, CYP2C19, CYP2C9) and N-acetyltransferase (NAT2) genotyping

k before administration and directly after completion of infusion

## FLOW CHART: REPEATED TREATMENT COURSES

Study Periods	Repeated treatment courses					EOT f	FU
	1	2	3	4	5		
Visit	1	2	3	4	5		
Day	1	2	8	15	22		
(day range)			(±1)	(±1)	(±2)		
Physical Examination	x g					x	x b
ECOG performance score	x					x	x
Pregnancy test	x						
MRI, CT a					x a		x
EUS, US (optional)					x		x
Body weight	x					x	
ECG	x k				x		x b
Infusion BI 6727	x						
Vital Signs	x	x	x	x	x	x	
Safety lab parameters	x g	x	x	x	x		x b
Urine examination	x g	x				x	
Pharmacokinetics (plasma)	x c	x c	x c	x c			
Adverse Events	x d	x	x	x	x	x	x e
Concomitant Therapy	x d	x	x	x	x		
Tumour assessment a					x a		x
Conclusion of Subject Participation						x	

a according to RECIST guidelines. Imaging and assessment are required at the end of every other treatment course.b optionalc for time schedule of pharmacokinetic sampling refer to table (Appendix 10.2), plasma samples have to be drawn from the opposite arm of the infusion. Intensive PK blood sampling performed in Course 1 only; for repeated courses PK blood sampling performed at the end of infusion (1:00h) after 24:00h, 168:00h and after 336:00h (Appendix 10.2).d update onlye if not yet recovered at the end of the previous course and in case of new adverse events if drug relatedf end of treatment; investigations which have to be performed at the last visit (when a patient discontinues the study)g data from last visit of previous course (day 22 ± 2) may be used in case examinations were done within the past four weeks

FU= follow up visit until progression, lost to follow up or treatment with another anti-cancer drug

k before administration and directly after completion of infusion of course 3 in eligible patients, further analyses in case of changes during prior courses

## ABBREVIATIONS

AE	Adverse Event
BI	Boehringer Ingelheim
CA	Competent Authority
CML	Clinical Monitor Local
CRA	Clinical Research Assistant/Associate
CRF/eCRF	Case Report Form / electronic Case Report Form
CTMF	Clinical Trial Master File
CRO	Clinical Research Organisation
CTP	Clinical Trial Protocol
CTR	Clinical Trial Report
DLT	Dose limiting toxicity
DNA	Desoxyribonucleic acid
ECC	Endogenous creatinine clearance
ECG	Electrocardiogram
ECOG	Eastern Cooperative Oncology Group
EDC	Electronic Data Capture
EDTA	Ethylenediaminetetraacetic acid
EOT	End of treatment
EUS	endoultrasonography
FDA	Food and Drug Administration
fe 0-24/48	Fraction of analyte eliminated in urine from time point 0 to time point 24/48
fe t1-t2	Fraction of analyte eliminated in urine from time point t1 to time point t2
FU	Follow up
GCP	Good Clinical Practice
gCV	geometric coefficient of variation
gMean	geometric mean
HR	heart rate
HPLC-MS/MS	High performance liquid chromatography, tandem mass spectrometry
ICH	International Conference on Harmonisation
IEC /EC	(Independent) Ethics Committee

IND	Investigational New Drug
INR	International normalised ratio
IRB	Institutional review board
ISF	Investigator Site File
LDH	Lactate dehydrogenase
MCV	Medium corpuscular volume
MRI	Magnetic resonance imaging
MRT	Mean residence time of the analyte in the body after intravenous administration
MTD	Maximum tolerated dose
NC	Next course
NOA	Not analyzed
NOP	No peak detectable
NOR	No valid result
NOS	No sample
No.	Number
OPU	Operative Unit (of BI)
PD	Progressive disease
PK	Pharmacokinetics
PLK-1	Polo-like kinase 1
PR	Partial response
PR-interval	interval between the beginning of the P wave and beginning of the Q wave (seconds). Also called the PQ interval
PT	Prothrombin time
PTT	Partial thromboplastin time
QRS	duration of the QRS wave form (seconds)
QT-interval	interval from the beginning of the Q wave to the end of the T wave on an ECG (seconds)
QTc	QT interval, corrected for heart rate (seconds)
QTcB	QT interval, corrected for heart rate according to Bazett's formula (seconds) = measured QT / (square root of preceding RR interval)
QTcF	QT interval, corrected for heart rate according to Fridericia's formula (seconds) = measured QT / (cube root of preceding RR interval)
RBC	Red blood cell count

RECIST	Response evaluation criteria in solid tumours
RR-interval	interval between R waves (seconds)
SAE	Serious Adverse Event
SD	Stable disease
SOP	Standard Operating Procedure
SUSAR	Suspected Unexpected Serious Adverse Reaction
$t_{1/2}$	terminal half-life of the analyte in plasma
$t_{max}$	time from dosing to maximum concentration

US	Utrasonography
$V_{ss}$	Apparent volume of distribution at steady state following intravascular administration
$V_z$	Apparent volume of distribution during the terminal phase $\lambda_z$ following an intravascular dose
WBC	White blood cell count

## 1. INTRODUCTION

### 1.1 MEDICAL BACKGROUND

Many advanced or metastatic human cancers are incurable despite the availability of a variety of conventional treatment modalities like surgery, cytotoxic drugs, radiation therapy, and combinations of these. Objective responses in patients with advanced disease, though frequently seen using conventional treatments, are often followed by tumour progression and death. Therefore the search for new therapeutic strategies has become an urgent priority.

Our understanding of cancer biology and cell cycle regulation in particular has increased considerably in recent years, preparing ground for novel targeted treatment principles. Mitotic kinases of the Polo family which are highly conserved in all eukaryotes have been identified as important regulators of cell division and its checkpoints (R04-0421). Polo-like kinase 1 (PLK-1) controls several key steps in the passage of cells through M phase:

1) initiation of entry into mitosis, 2) centrosome separation and maturation necessary for the formation of a bipolar mitotic spindle, 3) metaphase to anaphase transition and mitotic exit and 4) onset of cytokinesis (R04-0028). PLK-1 is a target of the DNA damage checkpoint (R04-0422). Failure of cell cycle checkpoints to arrest the cell after appropriate stimuli such as DNA damaging agents or radiation is a hallmark of cancer. These findings provide a rationale for pursuing PLK-1 inhibition as a therapeutic principle in oncology.

Recently mammalian PLK-1 was shown to be overexpressed in various human cancers such as non-small cell lung cancer (R04-0031) and colorectal cancer (R04-0034). The functional relevance of PLK-1 was demonstrated in *in vitro* “knock down” experiments where PLK-1 inhibition induced cell cycle arrest and apoptosis in cancer cell lines (R04-0030, R04-0423). A potential role for PLK-1 overexpression in carcinogenesis was shown both *in vitro* and *in vivo* (R04-0321). Therefore PLK-1 inhibition represents a promising new therapeutic approach with a novel mode of action in oncology.

The 1230.1 trial will investigate safety and preliminary efficacy of BI 6727, a highly selective and specific PLK-1 inhibitor to be administered intravenously to patients with advanced or metastatic cancers.

### 1.2 DRUG PROFILE

BI 6727 is a highly selective and potent small molecule Polo-like kinase 1 inhibitor. The pharmacological profile of BI 6727 was evaluated *in vitro* in enzymatic assays, cellular cytotoxicity assays and assays examining cell cycle progression. *In vivo* efficacy of BI 6727 was determined in human tumour xenografts in nude mice.

In an enzymatic assay using human recombinant PLK-1 the molecular potency of BI 6727 was in the low nanomolar range. More than 45 kinases tested in parallel with PLK-1 were not inhibited demonstrating the high molecular specificity of the compound. The compound was also tested for its cellular activity on a panel of tumour cell lines. Cytotoxicity *in vitro* and inhibition of PLK-1 in enzymatic assays was achieved at comparable concentrations. Activity was not dependent on cellular origin or molecular phenotype. Cell biological profiling revealed

that BI 6727 induces a typical PLK-1 mitotic arrest phenotype (G2/M arrest, abnormal mitotic figures) at similar concentrations. When comparing the activity in parental cell lines to the activity in the respective chemo-resistant counterparts activity of BI 6727 was much better conserved than the activity of conventional chemotherapeutics such as taxanes or vincristine.

Efficacy of BI 6727 was shown in various xenograft models. Tumour regression up to complete cures of animals was demonstrated. Tumour regression was also shown in models of larger tumours. Doses shown to be effective were well tolerated and were administered to nude mice 1-2 times per week intravenously.

The non-clinical safety profile of BI 6727 is considered favorable regarding the oncological indication and the antiproliferative principle. In 3-cycle toxicity studies in dogs and rats mechanism-related side effects were observed in organs with high turnover as expected. Main target organs were the gastrointestinal tract (mucosal lesions), bone marrow and lymphoid. Complete reversibility even of severe lesions at higher doses was observed. Moreover no evidence for unspecific toxicity affecting other organs such as kidney or liver was found. More detailed information is provided in the Investigator's Brochure.

No clinical data exist for BI 6727 administered to patients. Clinical data from the Polo-like kinase 1 inhibitor BI 2536 currently under investigation in clinical trials show good tolerability with haematotoxicity (neutropenia) constituting the dose limiting toxicity. No relevant unspecific toxicity has been observed as yet. Evidence for clinical antitumour activity has been observed.

### **1.3 RATIONALE FOR PERFORMING THE TRIAL**

This open label Phase I dose escalation trial 1230.1 is the first in man trial with BI 6727 in cancer patients. The trial will investigate safety and efficacy of this specific Polo-like kinase 1 inhibitor in cancer patients.

Patients with various solid tumours who have either failed conventional treatment, or for whom no therapy of proven efficacy exists, or who are not amenable to established forms of treatment will be treated with BI 6727 in this study. BI 6727 will be given as a single infusion over 60 minutes on day one of the study. Based on the 3-cycle non-clinical safety studies a recommended starting dose of 12 mg will be given.

Determination of the maximum tolerated dose (MTD) is the primary endpoint of this trial. MTD will be evaluated in patients receiving the first course of BI 6727. Depending on the drug related toxicity observed in this study three to six patients will be treated per dose tier. To increase the safety database at the MTD a total of 24 patients will be enrolled at MTD.

Secondary endpoints of this trial are safety, pharmacokinetic profile of BI 6727 and the assessment of antitumour efficacy.

Patients who experience a clinical benefit, i.e. an objective tumour response or symptom improvement or the absence of tumour progression and who have recovered from drug-related adverse events from previous courses are eligible for an additional course of BI 6727 according to protocol.

## 1.4 BENEFIT / RISK ASSESSMENT

Although considerable progress has been made in understanding cancer biology as well as in developing more effective treatment regimens, most patients with locally advanced or metastatic tumours will succumb to their disease. Thus, there is a substantial need for novel therapeutic strategies to improve the outcome for patients with advanced or metastatic malignancies who have failed conventional treatment, or for whom no therapy of proven efficacy exists.

Cell-cycle targeted therapies represent a novel and promising approach in these patients (R04-0415). Mitotic kinases regulating cell division and its checkpoints are considered particularly attractive targets for new therapies (R04-0421). BI 6727 represents a new class of small molecules targeting and blocking activation of PLK-1 with high selectivity and specificity. This compound induces cell cycle arrest, apoptosis and tumour shrinkage at tolerable doses in preclinical tumour models. In the clinical setting these effects may hopefully translate into tumour remissions in patients without further treatment options.

The most relevant side effect of BI 6727 administration is expected to be a transient inhibition of proliferation of normal dividing cells in mucosal tissue and bone marrow. Thymic atrophy seen in toxicological studies is not deemed relevant in the target population of adult cancer patients. Inhibition of mucosal proliferation may lead to gastrointestinal symptoms such as nausea or diarrhoea. The side effects on bone marrow stem cells may lead to a temporary decrease of blood cells and platelets. These side effects are frequently seen in cancer patients treated with conventional cytotoxics or targeted therapies and can easily be monitored. Supportive treatment for these effects is available. In contrast to many established antiproliferative agents no unspecific toxic effects have been identified for BI 6727 in preclinical studies. The QT-prolongation observed at high doses in an animal model are not expected to impair clinical development of the compound. Nevertheless ECG monitoring will be performed and analysed centrally by a core lab.

In ongoing clinical trials with the Polo-like kinase 1 inhibitor BI 2536 good tolerability has been demonstrated. Haematotoxicity with predominant neutropenia constituted dose limiting toxicity. The neutropenia was quickly reversible and did not accumulate after repeated courses in the patients treated so far. No unspecific toxicity, no toxicity relating to kidneys or liver and no cardio- or neurotoxicity have been documented so far. Evidence for antitumour efficacy has been observed.

Cancer patients with advanced tumours and no further treatment options may benefit from tumour shrinkage, tumour stabilisation or improvement of tumour-related symptoms induced by BI 6727. The potential benefit of therapy with BI 6727 is expected to outweigh the treatment related risks.

## 2. TRIAL OBJECTIVES

### 2.1 GENERAL AIM / PRIMARY OBJECTIVE

The primary objective of this trial is to identify the maximum tolerated dose (MTD) of BI 6727 therapy in terms of drug-related adverse events.

Secondary objectives are the collection of overall safety and antitumour efficacy data and the determination of the pharmacokinetic profile of BI 6727.

### 2.2 PRIMARY ENDPOINT

The primary endpoint of this trial is the determination of the Maximum Tolerated Dose (MTD) of BI 6727.

### 2.3 SECONDARY ENDPOINT(S)

- 1) Incidence and intensity of drug-related adverse events according to common terminology criteria for adverse events (CTCAE) v.3.0, laboratory evaluations, patient performance and vital signs
- 2) Tumour responses and time to progression after BI 6727 treatment
- 3) Pharmacokinetic parameters of BI 6727 (for parameters cf. section 7.1.2.).

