#### 4.1.3 Selection of doses in trial

##### 4.1.3.1. First course of administration of BI 6727

The starting dose will be 12 mg. As long as no patient of an ongoing dose tier develops drug-related toxicity beyond Grade 1 according Common Terminology Criteria for adverse events (CTCAE) during the initial treatment course the dose will be escalated by up to 100% in new patients. As soon as any patient of an ongoing dose tier experienced drug-related toxicity Grade 2 or higher escalation steps of not more than 50% will be allowed thereafter. Should dose limiting toxicity (DLT) be observed in 1/6 patients treated in a cohort and escalation continues this will be in steps of not more than 35%. Before entering patients at a higher dose level it will be ensured that all patients at an ongoing dose level have completed the initial course of BI 6727 dosing. The decision regarding the incremental size of the dose escalation steps will only be taken after discussion between the sponsor and the clinical investigator considering toxicity data from each patient cohort. Prior to inclusion of a new patient the investigator has to confirm the respective dose with the clinical monitor of the sponsor.

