7.7.1.2 Adverse events

AE analysis will be performed for all treatment periods and for the first treatment course.

The analyses of AEs will be descriptive in nature and will follow the standard procedure laid down in the DM & SM (including all required tables and listings) (current guideline [001-MCG-156](#) 'Handling and Summarization of AE Data for CTR and Integrated Summaries'). AEs will be coded with the most recent version of Medical Dictionary for Regulatory Activities (MedDRA version 10.0). The version number will be displayed as a footnote in the respective tables and listings. The system organ classes will be sorted according to the standard sort order specified by EMEA, preferred terms will be sorted alphabetically (within system organ class).

Each patient can be observed during the trial under several doses. Analysing the AE of all treatment courses will be carried out under the initial treatment. No formal statistical analysis is planned for the safety comparison.

The analysis of AEs will be based on the concept of treatment emergent AEs. AEs will be distinguished for the treatment course in which the subjects are on-treatment as well as for screening, and post-study [REDACTED] The actual

dosage of BI 6727 administered on the day each AE starts will also be derived and will be included in the listing. Listings of screening events will not be sorted by initial treatment ([Table 6.1.3: 1](#)). But post-study listings will be sorted by initial treatment.

According to the BI standards, multiple recordings of AEs will be collapsed to episodes on the lowest level term and multiple episodes will be condensed to records on the PT and system organ class (SOC) level. CTCAE grade will be an additional criterion for collapsing and condensing AEs. The maximum CTCAE grade will be assigned to episodes and records. CTCAE grade and DLT information will be displayed in AE listings. MedDRA levels for condensing will be SOC and PT.

According to ICH E3 (International Conference on Harmonisation Efficacy 3), AEs classified as 'other significant' will include those non-serious and non-significant AEs with

- (i) 'action taken = discontinuation' or 'action taken = reduced', or
- (ii) those identified by the Trial clinical monitor/Investigator at a BRPM.

An overall summary of AEs with additional columns 'CTCAE', 'DLT (yes/no)' and 'total' will be presented.

AE flags and attributes

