An AE flag will be defined for patients who developed an AE that was CTCAE grade ≥ 3 , DLT, or serious AE (SAE).

An AE attribute "CTCAE grade 3/4 or 5 combined with drug relation" will be derived to avoid incorrect condensing. Consider, for instance, a patient with coincident drug-related abdominal pain with CTCAE 1, and non-related vomiting with CTCAE 3. Without the new attribute these AEs would be reported as drug-related Grade 3/4 under the SOC Gastrointestinal disorder. With the new AE attribute these AE would be excluded.

An additional AE attribute "Drug relationship combined with seriousness of the AE" is needed similarly to the AE attribute "CTCAE grade 3/4 or 5 combined with drug relation" described above.

Frequency of patients with AEs will be summarised by treatment, primary SOC and PT. Separate tables will be provided for patients with other significant AEs, for patients with significant non-serious AEs and for patients with SAEs. Additionally, there will be a summary table presenting maximum CTCAE grade for each AE, as well as patients who developed AEs with CTCAE grade greater than 3, DLT, SAE, and significant AEs.

AE of special interest (User-defined AE categories): these will be the same as for project 1216.P1 (BI 2536). Frequency tables and listings for these AE categories will be provided.

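### SAP 7.7.1.2 stops drug relation being paired with another event's grade only for grades 3 to 5, so drug-related grade 1 can be shown as grade 2

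*Protocol*

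**What the plan says.** Protocol 2.3 lists as secondary endpoint 1 "Incidence and intensity of drug-related adverse events according to common terminology criteria for adverse events (CTCAE) v.3.0", together with laboratory evaluations, performance and vital signs. It sets no lower grade limit. Protocol 7.1.1 plans to report the incidence, severity and causality of adverse events by dose level, and Protocol 7.3.3 plans the distribution of patients by maximum CTCAE grade.

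SAP 7.7.1.2 sets the data handling. Recordings are collapsed to episodes, and "multiple episodes will be condensed to records on the PT and system organ class (SOC) level". On grade it says "CTCAE grade will be an additional criterion for collapsing and condensing AEs" and "The maximum CTCAE grade will be assigned to episodes and records". Drug relation is not named as a criterion for collapsing or condensing.

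Under AE flags and attributes, the same section describes the side effect. Its example is one patient with drug-related abdominal pain of grade 1 and unrelated vomiting of grade 3: "Without the new attribute these AEs would be reported as drug-related Grade 3/4 under the SOC Gastrointestinal disorder". The remedy is a derived attribute, "CTCAE grade 3/4 or 5 combined with drug relation", with which these events are excluded. A second attribute combines drug relationship with seriousness. No attribute covers grade 1 or 2.

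**The concern.** The mechanism in the SAP's example does not depend on the grade being 3. It operates whenever a related event and a higher-grade unrelated event fall in the same condensed record. With a related grade 1 and an unrelated grade 2 event in one SOC, the record is related (because of one event) and grade 2 (because of the other), and the planned attribute does not apply. A table of drug-related events by grade would then show drug-related grade 2 for a patient whose worst related event was grade 1.

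There is a second gap. When a patient with a related grade 1 or 2 event is excluded from the drug-related grade 3/4 count, the SAP does not say that the patient is then shown at grade 1 or 2.

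At stake is the intensity half of secondary endpoint 1 at the low grades. Overlap within a SOC is plausible: Protocol 1.4 expects nausea and diarrhoea, and the SAP's own example is gastrointestinal.

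**Working it through.** The plan gives no figure on this point to reproduce. The check applies the SAP's rule to all grade pairs and then sizes the effect under stated assumptions.

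**Step 1: the rule.** Let R be the grade of a patient's related event and U the grade of an unrelated event in the same SOC. Under plain condensing, the record is related with grade max(R, U). It is wrong whenever U > R. For R and U from 1 to 5 there are 25 pairs, of which 10 are wrong: (1,2), (1,3), (1,4), (1,5), (2,3), (2,4), (2,5), (3,4), (3,5), (4,5).

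**Step 2: the attribute.** It removes the false grade 3-or-higher label in 6 of the 10: (1,3), (1,4), (1,5), (2,3), (2,4), (2,5). Below grade 3, one pair stays wrong: (1,2), shown as related grade 2. The pairs (3,4), (3,5) and (4,5) may also stay wrong if the attribute is a single yes/no flag and these grades are tabulated separately. If the maximum is taken over related events only, 0 of 25 are wrong.

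**Step 3: size in one SOC.** Inputs: 24 patients at the MTD (Protocol 4.1.6). The rates below are assumptions, not figures from the documents, and R and U are taken as independent worst grades.

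- Related none/1/2/3+: 50/30/15/5%.
- Unrelated none/1/2/3+: 60/20/12/8% (A), or half as many unrelated events, 80/10/6/4% (B).

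The handling of excluded patients is not stated, so both readings are shown.

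*Excluded patients dropped from the by-grade table.* Shown grade 2 = P(R=1)·P(U=2) + P(R=2)·P(U≤2). Shown grade 1 = P(R=1)·P(U≤1). Missing = P(R=1 or 2)·P(U≥3).

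- A: grade 2 = 0.30×0.12 + 0.15×0.92 = 17.4%; grade 1 = 0.30×0.80 = 24%; missing = 0.45×0.08 = 3.6%.
- B: grade 2 = 0.30×0.06 + 0.15×0.96 = 16.2%; grade 1 = 0.30×0.90 = 27%; missing = 0.45×0.04 = 1.8%.
- Against a true 15%, the excess at grade 2 is 24×0.024 = 0.58 (A) or 24×0.012 = 0.29 (B) patients.

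*Excluded patients counted at their true related grade.* Nobody is missing, and only the (1,2) pair is wrong. Shown grade 2 = P(R=2) + P(R=1)·P(U=2).

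- A: 0.15 + 0.036 = 18.6%; grade 1 = 0.30 − 0.036 = 26.4%.
- B: 0.15 + 0.018 = 16.8%; grade 1 = 0.30 − 0.018 = 28.2%.
- The excess at grade 2 is 24×0.036 = 0.86 (A) or 24×0.018 = 0.43 (B) patients.

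**Step 4: sensitivity.** The number moved from grade 1 to grade 2 in one SOC is 24·a·b, where a is the share with related grade 1 as true maximum and b the share of these with unrelated grade 2 as well. For a from 20% to 60% and b from 5% to 30%, it runs from 24×0.20×0.05 = 0.2 to 24×0.60×0.30 = 4.3 patients. The upper end needs both extremes at once.

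**The case against.** The strongest reply is that no wrong table is actually specified. The SAP names a table of maximum CTCAE grade for each event, not stated to be limited to drug-related events, and it names no table of drug-related events at grades 1 and 2. Other tables follow a sponsor guideline that is not among the documents and may already filter on drug relation. That stands as far as it goes: the distortion is a consequence of the stated rule in any such table, not a demonstrated result. It does not remove the point, because the endpoint requires the intensity of drug-related events and the only rules in the SAP give a wrong grade for the (1,2) pair.

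The reach is also limited. The SAP's example involves two different preferred terms, so the error sits mainly in SOC rows. A preferred-term row is wrong only if the same patient has the same term both as related and, at a higher grade, as unrelated. Listings show CTCAE grade, DLT information and actual dose, so single events can be checked, although a listing does not replace a correct summary.

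A reader might infer more than the documents support:

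- *That patients are lost from the drug-related tables.* The SAP says only that such events are excluded, directly after referring to the false grade 3/4 report. Exclusion from that count is the natural reading; what happens next is unstated.
- *That the distortion is large at the level of any adverse event.* The SAP names SOC and preferred term as its condensing levels and states no rule for an overall row.
- *That dose escalation is affected, because drug-related grade 2 changes the permitted step.* Protocol 4.1.3.1 bases the step on sponsor–investigator discussion of each cohort's toxicity data, not on these tables. The MTD rests on DLTs, summarised separately in SAP 7.7.1.1.
- *That the seriousness attribute has the same flaw.* Seriousness is yes/no, so combining it with drug relation already resolves the pairing.

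**Conclusion.** The point holds as a partial correction of a defect that the SAP itself describes. In any table of drug-related events by grade, a related grade 1 event with an unrelated grade 2 event in the same SOC would be shown as drug-related grade 2. The SAP also leaves open at what grade patients excluded from the drug-related grade 3/4 count appear. The intensity part of secondary endpoint 1 can therefore be distorted at grades 1 and 2, mainly in SOC rows. Any-grade drug-related incidence, the first-course DLT summary, the MTD and the escalation decisions are not affected.

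The documents do not allow the size to be known. Under the assumed one-SOC rates and independence, drug-related grade 2 would be about 16–17% instead of 15%, roughly 0.3–0.6 of 24 patients, if excluded patients are dropped. It would be about 17–19%, roughly 0.4–0.9 patients, if they are counted at their true grade. The effect is small in most settings, but the analysis is descriptive, so the tabulated grade is itself the result and should be right.

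**What to change.** Add one rule to SAP 7.7.1.2: every table of drug-related adverse events by grade first selects the drug-related events and then takes the maximum CTCAE grade among those events, per patient, for all grades, at preferred-term and SOC level and in any overall row. This settles the (1,2) pair and shows patients excluded from the drug-related grade 3/4 count at their true related grade. The existing grade 3/4 or 5 attribute can stay, since under this rule it no longer has to carry the correction. The seriousness attribute needs no change.

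The cost is a sentence of SAP wording and a small programming change. Drug relation and grade are already collected for every event, so no new data are needed.
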